8.2 Handling of Potential Intercurrent Events

Potential intercurrent events considered in this study include 1) premature discontinuation of study drug and 2) initiation or dose escalation of CD-related corticosteroids defined in Section 8.2.2. Intercurrent events will be handled using the following methods for the efficacy analysis:

8.2.1 Premature Discontinuation of Study Drug

Data collected will be used regardless of premature discontinuation of study drug.

8.2.2 CD-Related Corticosteroid Therapy

The CD-related corticosteroids intercurrent event is defined as follows.

- Subjects not on CD-related corticosteroids (systemic or locally acting corticosteroids for CD) at baseline who initiated CD-related corticosteroids during the study;
- Subjects on CD-related systemic corticosteroids at baseline who have dosages increased to greater than the prednisone equivalent dose of corticosteroid taken at baseline, or initiation of any rectal corticosteroids during the study regardless of rectal corticosteroid dose;
- Subjects on CD-related rectal corticosteroids at baseline who have dosages increased to greater than the dose taken at baseline, or initiation of any new type of rectal or any systemic corticosteroids during the study.

The time point of the CD-related corticosteroids intercurrent event is defined as the earlier date when one or more of the scenarios above occurs for a subject. As such, all measurements at or after the occurrence of the CD-related corticosteroids intercurrent event through the end of the study will not be used in the analysis and will be handled as specified in [Appendix J](#).

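### The steroid intercurrent-event rule in SAP Section 8.2.2 omits subjects whose only baseline steroid is locally acting but not rectal, and so is narrower than the estimand it implements

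*SAP*

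**What the plan says.** SAP Section 8.2 names the events: "Potential intercurrent events considered in this study include 1) premature discontinuation of study drug and 2) initiation or dose escalation of CD-related corticosteroids". It leaves the definition of the second to Section 8.2.2, which lists three scenarios:

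- **No baseline steroid:** "Subjects not on CD-related corticosteroids (systemic or locally acting corticosteroids for CD) at baseline who initiated CD-related corticosteroids during the study".
- **Baseline systemic steroid:** "Subjects on CD-related systemic corticosteroids at baseline who have dosages increased to greater than the prednisone equivalent dose of corticosteroid taken at baseline". The only other trigger listed for these subjects is a rectal start, at whatever dose.
- **Baseline rectal steroid:** "Subjects on CD-related rectal corticosteroids at baseline who have dosages increased to greater than the dose taken at baseline". The other triggers listed here are a rectal steroid of a new type and the start of a systemic one.

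The time point of the event "is defined as the earlier date when one or more of the scenarios above occurs for a subject". Nothing outside the three scenarios can set it.

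Appendix J makes a subject a non-responder on the binary endpoints only from this event onwards. For the continuous ranked secondary endpoints it drops data after the event. The estimands in Sections 2.1 and 8.4.1 require response with neither a start nor a dose increase of Crohn's-related corticosteroids, and make no exception by steroid type or route.

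**The concern.** The first scenario counts a locally acting steroid as a Crohn's-related corticosteroid and names it beside, not within, the systemic class. The scenarios for baseline users then cover only systemic and rectal use. A user of a locally acting steroid given by another route is therefore too exposed at baseline for the first scenario, and on the wrong class of steroid for the other two.

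Both co-primary endpoints under both protocols are affected, as are the binary ranked secondary endpoints other than hospitalization and the continuous ranked secondary endpoints. Section 8.3.1 applies the same censoring rule in NRI-C, and NRI-NC differs only in how COVID-19 missingness is treated. Neither would catch these subjects. Responder status on a co-primary endpoint would then depend on how a programmer reads an incomplete list.

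**Working it through.** **Logic check.** Each baseline state is set against each on-study change, using only the wording of Section 8.2.2.

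| Only baseline Crohn's steroid | Dose above baseline | Systemic start | Rectal start | Non-rectal locally acting start |
|---|---|---|---|---|
| None | not applicable | event | event | event |
| Systemic | event (prednisone equivalent) | event only if the prednisone-equivalent dose exceeds baseline | event | not listed |
| Rectal | event | event | event if a new type | not listed |
| Non-rectal locally acting | not listed | not listed | not listed | not listed (new type) |

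The last row is empty. The last column is filled only for subjects on no steroid at baseline. For a baseline systemic user, the start of a non-rectal locally acting steroid might be caught if it were converted to prednisone equivalents, but the SAP does not say that it is. Under the estimand, every start or dose increase in the last row and last column should count.

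**Size.** The SAP has no figure for how many subjects use such steroids or escalate them, so all three inputs below are assumptions:

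- f = share of an arm in the uncovered group
- e = share of those who start or escalate a steroid
- r = share of those who then meet the endpoint

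Rise in the arm's response rate = f × e × r.

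- Low end: 0.02 × 0.05 × 0.20 = 0.0002, or 0.02 points.
- Middle: 0.10 × 0.15 × 0.50 = 0.0075, or 0.75 points.
- High end: 0.15 × 0.20 × 0.50 = 0.015, or 1.5 points. In the 171 placebo subjects this is 171 × 0.15 × 0.20 = 5.1 who escape the rule, about half of them counted as responders.
- If r is only the 12% placebo clinical remission rate assumed in Section 2.4, f from 0.05 to 0.15 with e = 0.20 gives 0.12 to 0.36 points.

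**Effect on the difference.** Take f = 0.10 and r = 0.50 in both arms.

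- Escalation 5% on risankizumab and 15% on placebo: 0.25 − 0.75 = −0.5 points.
- Escalation rates reversed: 0.75 − 0.25 = +0.5 points.
- Equal escalation: 0.

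**Effect on power.** Section 2.4 states 97% for 27.8% versus 12%, with 342 and 171 subjects, Fisher's exact test, two-sided 0.025. An exact calculation gives 97.7%, which agrees. With the high-end shift on placebo alone (12% + 1.5 = 13.5%) and risankizumab unchanged, it gives 93.4%. With a 0.5-point shift (12.5%) it gives 96.6%. The planned difference is 27.8 − 12 = 15.8 points.

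**The case against.** The strongest reply is that the gap depends on undefined terms. If locally acting means rectal in this SAP, or if every non-rectal locally acting steroid is classed as systemic and converted to prednisone equivalents, the scenarios are exhaustive. The protocol, not at hand, may say which steroids were allowed at baseline. It stands that the number of affected subjects is unknown and could be nil. But the SAP states neither reading. The first scenario separates locally acting from systemic, and the third uses the different word rectal. The contradiction with the estimand lies within the SAP.

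A second reply is that the As Observed analysis (Sections 8.3.2, 8.4.4 and 8.5.2, and Appendix J) uses all data whatever the steroid use. It shows results with no steroid rule at all and also changes the missing-data handling, so it neither implements the estimand nor isolates this group.

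Two stronger readings are tempting, and the document does not support them.

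- A reader might infer that escalation is commoner on placebo, so that the gap shrinks the treatment difference. Nothing in the SAP establishes that, and the sign can go either way.
- A reader might want Crohn's-related surgery, or a new Crohn's drug after stopping study drug, to count as non-response too. Section 8.2 names two events only, Section 8.2.1 uses data regardless of discontinuation, and surgery appears only as an additional endpoint in Section 3.3. Adding these would change the stated estimand. It would not correct an error.

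**Conclusion.** The point holds as a mismatch between rule and estimand. As written, Section 8.2.2 gives no event for subjects whose only baseline Crohn's steroid is locally acting and non-rectal. It also does not clearly cover baseline systemic or rectal users who add such a steroid. Baseline non-users are fully covered.

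The likely effect is small: about 0.02 to 1.5 points on an arm's response rate, resting entirely on assumed shares of 2% to 15% in the group, 5% to 20% escalating, and 20% to 50% of those meeting the endpoint. The upper figure is an extreme. The direction of any shift in the treatment difference is not established, and the power calculation is not seriously threatened. The point is worth correcting because it touches both co-primary endpoints, contradicts their estimands and is cheap to settle.

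**What to change.** Amend Section 8.2.2 as an analysis classification only; it changes nothing in how subjects are treated.

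1. Define three classes of Crohn's-related corticosteroid: systemic, non-rectal locally acting, and rectal. State to which class each recorded drug and route belongs.
2. Add a scenario for subjects on a non-rectal locally acting steroid at baseline. The event is a dose above baseline, or initiation of any systemic, any rectal or any new type of locally acting Crohn's-related steroid.
3. Add initiation of a non-rectal locally acting steroid to the scenarios for baseline systemic and baseline rectal users.
4. Keep the prednisone-equivalent test for systemic users. A blanket rule that any steroid not in use at baseline is an event would wrongly flag a switch between systemic steroids at an equal or lower equivalent dose.

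If the sponsor intends a reading under which the present scenarios are already complete, stating the class definitions would be enough.

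The cost is a few lines of SAP text and a revised flag built from concomitant medication data already collected. A few more subjects may become non-responders or lose later data in the MMRM. The wording should be fixed before the Week 12 lock and unblinding described in Section 8.1, since settling it afterwards would be a post hoc classification.

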8.3 Handling of Missing Data

Missing data could occur due to various reasons, including missing visits/assessments, early withdrawal from the clinical trials, or missing due to Coronavirus disease 2019 (COVID-19) infection or logistic restriction.

The COVID-19 pandemic is interfering with the conduct of many ongoing trials, with potential impacts on treatment duration and the collection, analysis, and the interpretation of clinical trial data. Some protocol-specified visits in the clinical trials may be impacted due to COVID-19 infection or logistical restrictions during the pandemic. For example, some scheduled visits may be missed due to self-quarantine or local government restrictions on travel; some visits may also be delayed or canceled due to healthcare resource constraints during the pandemic. Impacted visits due to COVID-19 will be

recorded in the database. The probability of having missed visits and missing data due to COVID-19 infection or logistical restrictions related to the COVID-19 pandemic can be reasonably assumed to be unrelated to the unobserved values. Therefore, for the purpose of statistical analysis, it is reasonable to assume that these missing data are missing at random (MAR) and the statistical models that require MAR assumption are appropriate. The intent is to provide reliable estimates of the treatment effects under the scenario without the impact of COVID-19 pandemic.

Missing data for the efficacy analyses will be handled using the methods described below. Handling of missing data in IBDQ and FACIT-Fatigue is shown in [Appendix F](#) and [Appendix G](#).

8.3.1 Categorical Endpoints

For binary efficacy endpoints, missing data will be handled using the following approaches:

- The primary approach for handling missing data in the analysis of binary endpoints will use **Non-Responder Imputation (NRI) while incorporating Multiple Imputation (MI) to handle missing data due to **CCOVID-19 (NRI-C)**.
 - The NRI-C will categorize any subject who does not have an evaluation during a pre-specified visit window (either due to missing assessment or due to early withdrawal from the study) as a non-responder for the visit. The only exception is that missing data due to COVID-19 infection or logistical restriction will be handled by MI. At each visit, subjects will be characterized as responders or non-responders based on MI imputed values if missing due to Covid-19, otherwise subjects will be considered as non-responder for missing due to other reasons in the NRI-C approach. Of note, subjects will be counted as non-responders thereafter and will not be imputed by MI after the CD-related corticosteroids censoring time point as specified in Section 8.2.2 and [Appendix J](#).**
- A sensitivity analysis for binary endpoints will use **NR**I with **No** special data handling for missing due to **CCOVID-19 (NRI-NC)**.

- NRI-NC will be performed in the same way as NRI-C without the exception above. Missing due to COVID-19 infection or logistical restriction will also be counted as non-responders. This is the same method as "NRI" as defined in the protocol.
- Details on MI method are described below:
 - Markov Chain Monte Carlo (MCMC) will be first applied to augment data into monotonic missing pattern, where applicable, and PROC MI will be used to generate 30 datasets using the regression method. If the binary endpoints are derived from the continuous variables, PROC MI will be applied to the continuous variables. The variables to be included in the imputation model are: treatment group, randomization stratification factors (Number of prior biologics failed (0, 1, > 1), baseline steroid use (Yes, No)), age, gender, weight and if applicable, baseline measurement and post-baseline measurements at each visit up to the end of the analysis period. The random seed for MCMC and the random seed for PROC MI are specified in [Appendix H](#). The imputed post-baseline measurements will be rounded to the same precision as the observed data before the determination of responder status. Prior to applying CMH model, subjects will be characterized as responders or non-responders based on MI imputed values if missing due to Covid-19, otherwise subjects will be considered as non-responder for missing due to other reasons in the NRI-C approach. Using the CMH model adjusted by randomization stratification factors, the endpoints will be analyzed using each of the 30 imputed datasets. SAS PROC MIANALYZE will be used to generate the final inferences of the risk difference between the risankizumab treatment group and placebo group, using Rubin's rule. The CD-related corticosteroid censoring rule, as specified in [Section 8.2.2](#) and [Appendix J](#), will be applied before and after applying MI for efficacy assessments.

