8.4.2 Handling of Missing Data for the Primary Efficacy Endpoint(s)

The NRI-C approach for handling missing data will be used for primary analysis for the co-primary endpoints for the 12-Week Induction Period.

The NRI-NC and PMM approaches for handling missing data will be conducted as sensitivity analyses for the co-primary endpoints for the 12-Week Induction Period if applicable. For PMM approach, the pre-specified missing-data patterns are given as below. Other missing data patterns could be explored if deemed necessary.

| Missing-data Patterns |
|---|
| Non-completers (missing at Week 4 or at Week 8 or at Week 12) |
| Completers |

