9.2.2 Adverse Event Overview

An overview of AEs will be presented consisting of the number and percentage of subjects experiencing at least one event for each of the following AE categories:

- Any treatment-emergent AE
- Any treatment-emergent AE related to COVID-19
- Any treatment-emergent AE related to study drug according to the investigator
- Any severe treatment-emergent AE
- Any serious treatment-emergent AE
- Any treatment-emergent AE leading to discontinuation of study drug
- Any treatment-emergent AE leading to death
- Treatment-emergent AEs of Safety Interest including
 - Adjudicated MACE events
 - Serious infections
 - Active Tuberculosis
 - Opportunistic infections excluding tuberculosis and herpes zoster
 - Malignant tumors
 - Malignancies excluding NMSC
 - Hypersensitivity – serious events only
 - Adjudicated anaphylactic reaction
 - Serious anaphylactic reaction
- All deaths
 - Deaths occurring \leq 140 days after last dose of study drug
 - Deaths occurring $>$ 140 days after last dose of study drug
 - Deaths related to COVID-19

The exposure adjusted rate for AE overview will be presented as well.

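### The COVID-19 exception in the primary missing-data rule (NRI-C) does not exclude death, so Week 12 response would be imputed for a subject who dies of COVID-19 before Week 12

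*SAP*

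**What the plan says.** SAP Section 8.3.1 defines NRI-C. Its default classes a subject who has no evaluation at the planned time, "either due to missing assessment or due to early withdrawal from the study) as a non-responder for the visit". One departure follows: "The only exception is that missing data due to COVID-19 infection or logistical restriction will be handled by MI". Section 8.3.1 then says how cases under the departure are resolved: "subjects will be characterized as responders or non-responders based on MI imputed values if missing due to Covid-19". The only limit on the departure is the corticosteroid rule, under which subjects "will not be imputed by MI after the CD-related corticosteroids censoring time point"; Section 8.3.1 applies that rule both before and after MI.

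Section 8.4.2 fixes the role of the method: "The NRI-C approach for handling missing data will be used for primary analysis for the co-primary endpoints". Section 8.5.1 also makes it primary for the binary secondary endpoints, apart from draining fistulas and CD-related hospitalization.

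Section 8.3 gives the justification. It takes "The probability of having missed visits and missing data due to COVID-19 infection or logistical restrictions" to be independent of what would have been measured, illustrates this with visits missed, delayed or cancelled, and states that the target is the treatment effect had there been no pandemic.

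Section 8.2 and Appendix J list two intercurrent events: stopping study drug early, and starting or escalating CD-related corticosteroids. Neither names death or a COVID-19 event. Section 9.2.2 nevertheless plans a count of "Deaths related to COVID-19".

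**The concern.** The default rule expressly reaches early withdrawal, so an exception to it reaches early withdrawal too. The exception is triggered by infection as well as by logistics, and nothing removes a subject who has died. The plan expects that COVID-19 deaths may occur, because it tabulates them.

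For a visit missed because a site was closed, a Week 12 value would have existed and missing-at-random is an arguable assumption about it. For a deceased subject there is no Week 12 value for the assumption to describe. Imputing one amounts to a hypothetical strategy for death that neither Section 2.1 nor Appendix J states. A reader of the estimand table could not tell that it was in force. Under Section 8.3.1, a subject who died of any other cause would be a non-responder.

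What is at stake is the definition of the co-primary estimand and the credibility of the responder count. Power is not threatened.

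**Working it through.** **Inputs, all from SAP Section 2.4 unless noted.** 342 risankizumab (one dose) against 171 placebo; Fisher's exact test, two-sided 0.025. Week 12 rates: clinical remission 27.8% and 12%; CDAI clinical remission 37% and 17%; endoscopic response 25.5% and 8%. Number of imputations: 30 (Section 8.3.1). The SAP gives no number of COVID-19 deaths or withdrawals, so the affected share f is an assumption, taken as 1% to 3%.

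**Planned power.** Exact enumeration of Fisher's test gives 97.7% for clinical remission (stated 97%), 99.5% for CDAI clinical remission (stated 99%) and 99.8% for endoscopic response (stated 99%). The planning figures reproduce.

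**Credit per affected subject.** Ignoring covariates, an imputed subject is a responder in an expected 30 × p of the datasets, where p is the arm's rate:

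| Endpoint | Risankizumab | Placebo |
|---|---|---|
| Clinical remission | 30 × 0.278 = 8.3 | 30 × 0.12 = 3.6 |
| CDAI clinical remission | 30 × 0.37 = 11.1 | 30 × 0.17 = 5.1 |
| Endoscopic response | 30 × 0.255 = 7.7 | 30 × 0.08 = 2.4 |

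Averaged over the 30 datasets, the subject therefore contributes a fraction p of a response instead of 0.

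**Shift in the treatment difference.** NRI-C minus non-response handling equals f(active) × p(active) − f(placebo) × p(placebo). In percentage points, for f = 1% and f = 3%:

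| Endpoint | Both arms equally | Risankizumab only | Placebo only |
|---|---|---|---|
| Clinical remission | +0.16 to +0.47 | +0.28 to +0.83 | −0.12 to −0.36 |
| CDAI clinical remission | +0.20 to +0.60 | +0.37 to +1.11 | −0.17 to −0.51 |
| Endoscopic response | +0.18 to +0.53 | +0.26 to +0.77 | −0.08 to −0.24 |

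For example, both arms equally on CDAI clinical remission: 1% × (37 − 17) = 0.20 and 3% × (37 − 17) = 0.60.

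**Direction.** The shift is zero when f(placebo) / f(active) = p(active) / p(placebo): 27.8 / 12 = 2.3, 37 / 17 = 2.2 and 25.5 / 8 = 3.2. Below that ratio NRI-C favours risankizumab; above it, placebo.

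**Effect on power.** With f = 1% in both arms (about 3.4 risankizumab and 1.7 placebo subjects), counting them as non-responders takes the clinical remission difference from 15.80 to 15.64 points and Fisher power from 97.7% to 97.5%. Even at f = 5% the figures are 15.01 points and 96.8%.

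**The case against.** The strongest reply is that Section 8.3 declares a no-pandemic target. Under it, infection is as much a pandemic effect as a closed site, and treating it differently from other infections is coherent. This stands for visits missed through infection by subjects who survive and stay in the study: MI there is a defensible choice. It does not settle death, for which the plan gives no argument, and the target is not carried into Section 2.1 or Appendix J.

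A second reply is that the plan never says a deceased subject will be imputed, and that its examples concern missed visits, so permanent withdrawal might be meant to stay under non-response. That is a possible reading of Section 8.3. It sits badly with Section 8.3.1, where the exception is attached to a rule that names early withdrawal. The imputation of deaths follows from the rule as written together with its silence, not from an explicit statement.

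Three stronger readings are tempting and are not supported:

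- That such a subject simply counts as a responder. The subject is one in only some of the 30 datasets, the imputation model uses the subject's own earlier visits where applicable, and a prior corticosteroid event rules it out.
- That the rule always favours risankizumab or turns a safety harm into efficacy. The sign depends on the balance between arms, and nothing in the SAP shows more COVID-19 on active drug; listing serious infections as an area of safety interest does not show it.
- That anyone who withdraws while infected is imputed. The data must be missing because of COVID-19.

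Finally, NRI-NC is pre-specified for the co-primary endpoints and counts all COVID-19 missing data as non-response. It therefore gives a lower limit for each arm's rate. It does not isolate deaths, because it also turns logistical misses into non-response.

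**Conclusion.** The point holds in a narrow form. Applied literally, NRI-C imputes Week 12 response for a subject who died of COVID-19, and no estimand attribute says so or justifies it. How permanent withdrawal due to COVID-19 infection is handled should likewise be settled in the estimand. MI for infection-related missed visits in continuing subjects is not at fault.

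The size is small: about 0.2 points of treatment difference per 1% of both arms affected, against planned differences of 15.8 to 20 points. This rests on an assumed affected share, on arm-level planning rates applied without covariates, and on equal shares in the two arms; unequal shares can move the result either way. NRI-NC bounds it. Severity is low: this is a gap in the estimand and the rule, to be closed by clarification.

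**What to change.** In Sections 8.2 and 8.3.1 and in Appendix J:

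- Count a subject as a non-responder from the date of death, COVID-19 death included, applied before and after MI in the same way as the corticosteroid event.
- For permanent withdrawal from study due to COVID-19 infection, either count it as non-response or write the hypothetical no-pandemic strategy into the estimand and justify it.
- Keep MI for visits missed through logistical restrictions or temporary infection in subjects who stay in the study.
- Carry the same wording to the binary secondary endpoints that use NRI-C.

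The cost is a few sentences and some derivation code. Response rates may be marginally lower. Section 8.3 says that visits affected by COVID-19 are recorded, but not that infection and logistics are coded apart, so the sponsor must confirm that the data allow the distinction.

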3.2 Secondary Endpoint(s)

For US-specific protocol, the secondary endpoints under overall type I error control are:

1. The achievement of clinical remission at Week 12
2. The achievement of CDAI clinical response at Week 4
3. The achievement of CDAI clinical response at Week 12

4. Change from baseline in Functional Assessment of Chronic Illness Therapy-Fatigue (FACIT-Fatigue) at Week 12
5. The achievement of CDAI clinical remission at Week 4
6. The achievement of CDAI clinical response and endoscopic response at Week 12
7. The achievement of SF remission at Week 12
8. The achievement of AP remission at Week 12
9. The achievement of endoscopic remission at Week 12
10. The achievement of enhanced clinical response at Week 4
11. The achievement of ulcer-free endoscopy at Week 12
12. The achievement of enhanced clinical response at Week 12
13. The achievement of resolution of extra-intestinal manifestations (EIMs) at Week 12, in subjects with any EIMs at baseline
14. Occurrence of CD-related hospitalization through Week 12
15. The achievement of no draining fistulas at Week 12 in subjects with draining fistulas at baseline

For global protocol outside US, the secondary endpoints under overall type I error control are:

1. The achievement of CDAI clinical remission at Week 12
2. The achievement of CDAI clinical response at Week 4
3. The achievement of clinical remission at Week 4
4. The achievement of CDAI clinical response at Week 12
5. Change from baseline in FACIT-Fatigue at Week 12

6. Change from baseline in Inflammatory Bowel Disease Questionnaire (IBDQ) total score at Week 12
7. The achievement of enhanced clinical response and endoscopic response at Week 12
8. The achievement of endoscopic remission at Week 12
9. The achievement of enhanced clinical response at Week 4
10. The achievement of ulcer-free endoscopy at Week 12
11. The achievement of enhanced clinical response at Week 12
12. The achievement of resolution of EIMs at Week 12, in subjects with any EIMs at baseline
13. Occurrence of CD-related hospitalization through Week 12
14. The achievement of no draining fistulas at Week 12 in subjects with draining fistulas at baseline
15. Change from baseline in Work Productivity and Impairment Questionnaire – Crohn's disease (WPAI-CD) Overall Work Impairment at Week 12
16. Change from baseline in Short Form-36 (SF-36) Physical Component Summary (PCS) score at Week 12

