7.1 Demographics and Baseline Characteristics

The following demographic and baseline or disease characteristics will be summarized at the baseline of the study, where the baseline refers to the last non-missing observation before the first administration of any study drug.

Demographics

- Age (years)
- Age category [< 18 , [18, 40), [40, 65), ≥ 65]
- Sex [male/female]
- Race [American Indian/Alaska Native, Asian, Black or African American, Native Hawaiian or Other Pacific Islander, White, Multiple]
- Ethnicity [Hispanic/Latino, Non-Hispanic/Latino]
- Geographic region (as defined in [Appendix I](#))

Tobacco/Nicotine and Alcohol Use

- Tobacco/Nicotine Use [currently smokes, ex-smoker, never smoked, unknown]
- Alcohol Use [current drinker, former drinker, non-drinker, unknown]

Vital Signs

- Systolic and diastolic blood pressure (mmHg)
- Pulse (bpm)
- Body temperature (°C)
- Body weight (kg) – overall and by sex
- Body weight category (< 60 kg, ≥ 60 kg)
- Height (cm)
- Body Mass Index (kg/m²)
- BMI Category
 - Underweight [< 18.5 kg/m²]
 - Normal [≥ 18.5 and < 25 kg/m²]
 - Overweight [≥ 25 and < 30 kg/m²]
 - Obese [≥ 30 kg/m²]

Patient Reported Outcomes at Baseline

- IBDQ – total score and domain scores
- WPAI-CD – 4 sub-scores
- CSS – total score
- FACIT-Fatigue – total score and 13 item scores
- EQ-5D-5L – Index score and Vas Pain
- SF-36 – 8 domain scores, PCS and MCS
- Average Daily Stool Frequency
- Average Daily Abdominal Pain

Other Assessments at Baseline

- CDAI
- SES-CD
- Crohn's Disease Duration (years)
- Fecal calprotectin
- Baseline corticosteroid use (yes, no)
- Baseline immunomodulator use (yes, no)
- Biologics failure history (0, 1, >1)
- TNF failure history (0, 1, >1) within bio-IR population
- Vedolizumab failure history (yes, no) within bio-IR population
- Ustekinumab failure history (yes, no) within bio-IR population
- hs-CRP
- Draining fistulas (yes, no)
- Non-draining fistulas (yes, no)
- Anal fissures (yes, no)
- Crohn's Disease Location Per SES-CD (colonic only, ileal only, ileal-colonic)
- Extra Intestinal Manifestation (yes, no)

In addition, some clinical tests at baseline such as TB test, pregnancy test and electrocardiogram assessment will be summarized. Crohn's Disease history (Montreal classification) and Crohn's Disease surgical history will be summarized separately as well.

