Appendix H. Random Seeds

In case of non-convergence, the random seed will be updated by adding 100000 at each attempt until convergence of model happens.

Table H-1. Random Seeds for NRI-C

| Variables | Random Seed | |
|--------------------------------------|----------------|---------|
| | MCMC Procedure | PROC MI |
| CDAI | 50001 | 60001 |
| SES-CD (for 20 individual variables) | 50002 | 60002 |
| SF score | 50003 | 60003 |
| AP score | 50004 | 60004 |
| EIM | 50005 | 60005 |
| FACIT-Fatigue | 50006 | 60006 |
| IBDQ total score | 50009 | 60009 |
| PGIS | 50010 | 60010 |
| PGIC | 50011 | 60011 |

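### NRI-C imputes yes/no EIM status with a method for continuous data plus rounding; the effect on a ranked secondary endpoint is small, but a binary imputation model should be named

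*SAP*

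**What the plan says.** Section 8.3.1 limits multiple imputation under NRI-C to values missing because of COVID-19; every other missing value counts as non-response. It gives one imputation recipe for all variables:

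- "Markov Chain Monte Carlo (MCMC) will be first applied to augment data into monotonic missing pattern, where applicable"; then
- "PROC MI will be used to generate 30 datasets using the regression method"; then
- "The imputed post-baseline measurements will be rounded to the same precision as the observed data before the determination of responder status".

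The only sentence that depends on variable type is "If the binary endpoints are derived from the continuous variables, PROC MI will be applied to the continuous variables". Nothing is said for a variable that is itself binary.

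That open case is used. Table H-1 in Appendix H, the seed table for NRI-C, contains the row "EIM | 50005 | 60005", so EIM has both an MCMC seed and a PROC MI seed. Section 7.1 lists EIM among the baseline characteristics as yes/no. The coding of post-baseline EIM in the imputation is not given.

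EIM resolution at Week 12 is under type I error control in both testing schemes of Section 3.2: 13th for the US ("The achievement of resolution of extra-intestinal manifestations (EIMs) at Week 12, in subjects with any EIMs at baseline") and 12th outside the US ("The achievement of resolution of EIMs at Week 12, in subjects with any EIMs at baseline"). Section 8.5.1 makes NRI-C primary for categorical secondary endpoints and excepts only CD-related hospitalization and draining fistulas, so EIM resolution falls under NRI-C.

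**The concern.** MCMC and the regression method draw from a normal model. For CDAI, stool frequency, abdominal pain and similar scores this is a usual choice, because the responder cut-off is applied to a plausible score. For a 0/1 variable it is not. A normal draw rounded to the nearest integer does not reproduce the underlying proportion, and some draws round to -1 or 2. The SAP has no rule assigning such a value to resolved or not resolved, so two programmers could follow the text and obtain different primary results. A logistic imputation model in the same SAS procedure avoids both problems. At stake is the accuracy and reproducibility of the primary analysis of one alpha-controlled secondary endpoint.

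**Working it through.** The SAP gives no EIM rate, no number of subjects with EIMs at baseline and no COVID-19-missing fraction, so there is no stated figure to reproduce. The rates and missing fractions below are assumptions, shown over a range.

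**Step 1: imputed rate.** Code EIM 1 = present, 0 = resolved. Let r be the true resolution rate, so the mean is m = 1 - r and SD = sqrt(r(1 - r)). Without covariates, and counting rounded values of 0 or below as resolved:

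- imputed resolution rate = Phi((0.5 - m)/SD) = Phi((r - 0.5)/SD)
- share outside 0/1 = Phi((-0.5 - m)/SD) + 1 - Phi((1.5 - m)/SD)

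For r = 0.30: SD = sqrt(0.30 × 0.70) = 0.458. The imputed rate is Phi(-0.2/0.458) = 33.1%. The share outside 0/1 is 0.44% + 4.04% = 4.5%.

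| True r | Imputed rate | Error (points) | Outside 0/1 |
|---|---|---|---|
| 10% | 9.1% | -0.9 | 2.3% |
| 20% | 22.7% | +2.7 | 4.1% |
| 30% | 33.1% | +3.1 | 4.5% |
| 40% | 41.9% | +1.9 | 4.6% |
| 50% | 50.0% | 0.0 | 4.6% |
| 60% | 58.1% | -1.9 | 4.6% |

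For r from 10% to 60% the largest error is +3.2 points, at r of about 27%. A logistic model without covariates has expected imputed rate r and yields only 0 or 1.

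**Step 2: the unstated mapping.** If only an exact 0 counts as resolved, the error at r = 60% is -5.2 points instead of -1.9, and at r = 70% it is -7.2 instead of -3.1.

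**Step 3: treatment difference.** Only the COVID-19-missing fraction f is imputed, so the shift in the overall difference is f × (imputed difference - true difference). For 10% vs 20%: imputed difference = 22.66 - 9.12 = 13.54 points, an excess of 3.54, and 0.10 × 3.54 = +0.35.

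| True rates | f = 2% | f = 5% | f = 10% |
|---|---|---|---|
| 10% vs 20% | +0.07 | +0.18 | +0.35 |
| 20% vs 35% | 0.00 | 0.00 | 0.00 |
| 25% vs 45% | -0.04 | -0.11 | -0.22 |
| 30% vs 40% | -0.02 | -0.06 | -0.12 |

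For any pair of rates between 10% and 60%, the errors span -1.91 to +3.22, so the shift at f = 10% cannot exceed 0.10 × 5.13 = 0.51 points in this covariate-free calculation.

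**Step 4: simulation with covariates.** Linear-regression imputation used treatment and Week 4 and Week 8 EIM, over 400 trials of 30 imputations, with 342 vs 171 subjects, an assumed 45% with EIM at baseline and 10% missing. Values of 0 or below counted as resolved. Errors in the imputed rates by arm ran from about -5 to +3 points. The largest between-arm discrepancy was for 10% vs 20% with the model fitted in all subjects: placebo 10.1% against a truth of 9.8% (+0.3), risankizumab 14.4% against 19.5% (-5.1). That is -5.4 points, or 0.10 × -5.4 = -0.54 on the overall difference. The share outside 0/1 was 2.6% to 5.0% when fitted in subjects with baseline EIM and 0.9% to 1.3% when fitted in all subjects.

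**The case against.** The strongest reply is that the text is incomplete rather than wrong. Section 8.3.1 never says normal or linear, and the 0/1 coding is inferred from a baseline list. Item 4 of the CDAI (Appendix D) counts categories of complaint, so EIM might be carried as a count. This stands in part: both points are inferences. But the rounding step and the MCMC seed for EIM fit continuous draws and not logistic ones, a small count with many zeros would also suit a normal model poorly, and the missing coding is itself part of the gap.

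Second, the plan limits the damage. Imputation touches only COVID-19-missing values. NRI-NC is a pre-specified sensitivity analysis for this endpoint (Section 8.5.1) and the as-observed analysis is repeated (Section 8.5.2). A pattern mixture model is also planned as appropriate. Dependence on the imputation model would show. This stands in full and keeps the point minor.

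Three stronger readings are not supported:

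- A reader might infer that the ranked endpoint itself takes impossible values. It does not: values of -1 or 2 arise in the intermediate EIM variable, and responder status is set afterwards.
- A reader might infer a consistent bias in one direction. The error changes sign with the rate and can be zero.
- A reader might extend the point to PGIS and PGIC, which also have seeds in Table H-1. Section 8.6 analyses their response endpoints as observed, and no PGIS or PGIC endpoint is ranked.

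**Conclusion.** The point holds as a minor, correctable weakness. Followed as written, Section 8.3.1 and Table H-1 apply a continuous-data method to a variable the SAP lists as yes/no, in the primary analysis of an alpha-controlled endpoint. If EIM is coded 0/1, the imputed resolution rate is off by a few points for most rates, and a few percent of intermediate draws have no assigned responder status. On the treatment difference this amounts to a few tenths of a point, and about half a point at most in the scenarios examined with values of 0 or below counted as resolved. These sizes rest on an assumed COVID-19-missing fraction of up to 10% and on assumed resolution rates. The SAP supplies neither, and nothing here shows that a conclusion would change.

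**What to change.** In Section 8.3.1, state that EIM is coded as binary and that its COVID-19-missing values are imputed with PROC MI FCS LOGISTIC, without the preceding MCMC step. Keep the regression method for the continuous scores. MONOTONE LOGISTIC after the MCMC step would not be enough, because that step would still fill non-monotone gaps with normal draws. The cost is a sentence or two, a changed EIM row in Table H-1 (the MCMC seed falls away) and a different statement in the same procedure.

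The alternative is to make NRI-NC primary for EIM, as Section 8.5.1 already does for draining fistulas. It is simpler but not neutral. With 10% COVID-19-missing in both arms (assumed), true rates of 25% and 45% would become 22.5% and 40.5%. The difference of 20 points would fall to 18, a larger shift than the -0.22 points it replaces. FCS LOGISTIC is therefore the better choice unless the number of subjects with EIMs at baseline is too small to support it.
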